8.2.13 Antibodies

Pure red cell aplasia (PRCA) in association with neutralizing antibodies to native erythropoietin has been observed in patients treated with recombinant erythropoietins. This has been reported predominately in patients with chronic renal failure. PRCA has been reported in a limited number of subjects exposed to other recombinant erythropoietin products prior to exposure to darbepoetin alfa; therefore, the contribution of epoetin alfa to the development of PRCA is unclear. Any patient with loss of response to rhu-erythropoietin should be evaluated for the etiology of loss of effect. Rhu-erythropoietin should be discontinued in any patient with evidence of PRCA and the patient evaluated for the presence of binding and neutralizing antibodies to epoetin alfa, native erythropoietin, and any other recombinant erythropoietin administered to the patient. In patients with PRCA secondary to neutralizing antibodies to erythropoietin, epoetin alfa should be discontinued. (Source for reviewer: USPI)

Serological screening to investigate the presence of neutralizing antibody to epoetin alfa can be arranged by contacting Janssen Products, LP, at [name].

All occurrences of PRCA, loss of effect (LOE) of epoetin alfa in the treatment of anemia and/or a report of the presence of antibodies to erythropoietin, will be defined as a SAE and reported and tracked as such.

Any patient who develops a sudden loss of response to epoetin alfa therapy, (unexplained drop in Hb >2g/dL), accompanied by a low reticulocyte count should be appropriately evaluated for etiology (e.g. iron or vitamin deficiency, blood loss, hemolysis, infection or inflammation, progression of underlying malignancy, aluminum intoxication). In the absence of another etiology, serum should be tested for the presence of antibodies to erythropoietin.

In the event that erythropoietin testing is deemed necessary in the setting of PRCA, a consent form for the testing of erythropoietin antibodies is required. Refer to [Appendix](#), Addendum 1.

8.2.14 Pregnancy and Lactation

There are no adequate and well-controlled studies in pregnant women (pregnancy category C); therefore, epoetin alfa should not be used during pregnancy. In addition, it is not known if epoetin alfa is excreted in human milk, therefore, lactating mothers should stop nursing before participating in any epoetin alfa study.

8.2.15 Geriatric Use

Please refer to the epoetin alfa drug insert for specific information on geriatric use.

Rev. 6/13
Rev. 5/17

Rev. 6/11

The overall goal of this study is to improve the rate of MER through combined therapy of lenalidomide and epoetin alfa (arm B) by 20% over that of arm A of lenalidomide monotherapy, in which the rate of MER is estimated at 30%, in an MDS population without chromosome 5q31.1 deletion. The anticipated improvement in response is based upon the potentiation of erythroid colony-forming capacity in cell line models. MER will be evaluated at 16 weeks after start of study treatment. Patients without 5q31.1 deletion will be randomly assigned to one of two treatment arms, stratified by serum erythropoietin level (≤ 500 mU/mL vs. > 500 mU/mL) and prior erythropoietin/DA treatment (yes vs. no). Patients with 5q31.1 deletion will be assigned to arm A only for correlative studies, and will not be included in the comparative analysis of the study. The original design required 236 total patients (212 to be randomized) in order to obtain 80% power for the primary comparison. Due to an interruption in drug supply, the study was suspended and epoetin alfa treatment was held on September 24, 2010. At that time, 67 patients were enrolled. Among them, 57 were randomized (29 on arm A, 28 on arm B). 7 patients on Arm B were still within 16 weeks treatment. New supply of epoetin alfa was available for arm B patients on October 27, 2010 and the study was reopened on February 4, 2011. Due to this unexpected drug supply issue, the comparison of the primary endpoint may lose some power. To minimize the potential effect on the primary endpoint, in the revised design, 14 patients (7 on arm A; 7 on arm B) randomized between May 19, 2010 and September 24, 2010 will be excluded from the primary analysis. The total accrual will be increased to 252 (226 to be randomized). This revised statistical considerations section is to incorporate this change.

9.1 Accrual

This study requires 212 patients (226 to be randomized) without 5q31.1 deletion for the primary endpoint comparison. Assuming that 10% of patients in the MDS population as defined in this study have the 5q31.1 deletion, a total of 252 patients will be entered. Accrual for E1996, a previous study in this patient population was lower than expected. However, since the proposed regimens (lenalidomide, lenalidomide + epoetin alfa) are different from the regimen used in E1996 (erythropoietin vs. supportive care) with promising activity in multi-center phase II trials, and this study will be an intergroup study, we anticipate no accrual impediment. In fact, based on the accrual to the study before its suspension, we anticipate that the accrual rate will be approximately 60 patients per year, and thus, the accrual will be completed in approximately five years, taking the suspension time into account. The feasibility of achieving the accrual goal will be monitored closely by the ECOG-ACRIN Data Monitoring Committee (DMC) and the NCI. According to NCI guidelines, if quarter 5-6 accrual (the number of patients enrolled on trial during quarters 5 and 6 after activation) is $\leq 20\%$ of projected rate, then the trial will be closed; If quarter 5-6 accrual is $< 50\%$ and $> 20\%$ of projected rate, then the study team will be given 6 months to improve accrual. If the average accrual rate in quarter 8 is below 50% then the trial will have to be amended to reflect actual accrual.

9.2 Primary Endpoint

The primary endpoint in this phase III study of previously erythropoietin/DA-treated MDS patients or erythropoietin/DA-naïve patients but with high transfusion frequency or high endogenous erythropoietin level is major erythroid

response (MER), defined as sustained transfusion independence in transfusion-dependent patients or a rise in hemoglobin > 2 g/dL in transfusion-independent patients with anemia for a minimum of eight consecutive weeks. The objective MER will be assessed 16 weeks after start of study treatment. At the time of objective MER assessment, patients who fail to achieve MER on Arm A will be allowed to crossover to Arm B.

When patients were treated with lenalidomide alone in phase II trials, the MER rates were 25%-34% in patients without a chromosome 5q31.1 deletion and 67% with a chromosome 5q31.1 deletion. There is limited clinical information for the combination of lenalidomide with epoetin alfa. In a pilot study involving 40 patients that had failed erythropoietin monotherapy, 5 of 18 patients who received the lenalidomide and epoetin alfa combination treatment achieved an erythroid response after failing to respond to lenalidomide alone, including 3 MER (12). When UT7 erythroid progenitor cells are treated with lenalidomide and in vitro, clonogenic response and STAT5 activation is additive or greater. Thus, we anticipate that MER rate for the combination of lenalidomide with epoetin alfa will be even higher. Based on this information, we hypothesize that the MER rate in Arm A (lenalidomide) will be 30% and anticipate that the MER rate in Arm B (lenalidomide + epoetin alfa) will be at least 50%. Thus the study is designed to detect an improvement of 20% in the MER rate from 30% to 50%, comparing Arm A to Arm B. Using the statistical package EaSt (Cytel Software Corporation, 1993) to account for multiple interim looks in a sequential design for binomial distribution with continuity correction, a sample size of 212 cases will provide approximately 80% power to detect improvement in MER rate with an overall one-sided type I error rate of 0.025. The primary comparison of the MER rates will be performed on all patients randomized before May 19, 2010 and after September 24. The 14 patients (7 on arm A; 7 on arm B) randomized between May 19, 2010 and September 24, 2010 will be excluded. A secondary analysis will include all 226 patients randomized to this study.

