7.1 Therapeutic Parameters

1. All CBCs and RBC transfusion values for the eight weeks prior to randomization are required to establish transfusion-dependence and baseline hemoglobin. Transfusion number and dates must be documented for the eight weeks preceding initiation of study treatment.
2. For non-transfusion dependent patients (i.e., receiving < 2 units/4 weeks x 8 weeks pre-study) who receive periodic transfusions, the mean pre-transfusion hemoglobin should be used to determine protocol eligibility and response reference.

NOTE: For non-transfusion dependent patients, a minimum of 2 pre-transfusion or un-transfused hemoglobin values are required.

3. [Deleted in Addendum #4]
4. All required prestudy chemistries, as outlined in Section [3](#) (at least one set of the two required sets), should be done within 7 days before randomization. CBC/Diff and chemistries should also be performed on Day 1 of each cycle.
5. Prestudy non-transfused Hgb, Hct, WBC, ANC, Plt should be documented on **2 occasions over 56 days** prior to randomization. The 2 occasions must be separated by at least 7 days.

Response Assessment

Hematologic, pathologic and cytogenetic response will be assessed according to criteria outlined in Section [6.1.2](#).

NOTE: When recording prestudy results on the ECOG-ACRIN forms, please make sure that ALL relevant dates are clearly given. Do **not** put all the results under the date for Day 1 of protocol treatment unless they were actually done that day. Record the actual dates.

Rev. 10/09,
6/11

Rev. 10/09

Rev. 10/09 Rev. 4/15	Assessment	Screening ¹ (56 days prior to randomization unless otherwise noted)	Weekly	Day 1 of each cycle ¹⁵	Every 8 weeks ¹⁵	Week 16 and Treatment Discontinuation	Follow-Up
	Medical History	X					
	Prior MDS Treatment	X					
	ECOG Performance Status	X		X		X	
	Pregnancy test ²	X ³		X ⁴		X	
	Physical examination	X ⁹		X			
	ECG	X					
Rev. 6/13 Rev. 10/09	Thyroid function tests ⁵	X				X	X ¹¹
Rev. 6/11	Serum erythropoietin (when Hgb < 9.5 g/dL pre-study)	X			X	X	
Rev. 10/09	Serum chemistry ^{6,7}	X		X		X	X ¹¹
Rev. 10/09	Hematology ⁸	X	X ¹⁰	X ⁹		X	X ¹¹
	RBC Transfusion History ⁸	X					
	Serum ferritin level				X		
Rev. 10/09	Response assessment ¹³			X	X	X	X ¹¹
Rev. 10/09 6/11	Toxicity assessment ¹⁴		X	X	X	X	X ¹¹
Rev. 10/09	Bone marrow aspirate & biopsy ¹²	X				X	X

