9.3 Secondary Objectives

All analyses on secondary endpoints will be performed on 212 patients randomized before May 19, 2010 and after September 24. The 14 patients (7 on arm A; 7 on arm B) randomized between May 19, 2010 and September 24, 2010 will be excluded.

Time to MER is defined in responders as the time from randomization to the documented date of MER. For transfusion independent patients, the date of MER is the first date of the elevation in hemoglobin level of more than 2 g/dL that has been sustained for at least 8 weeks. For transfusion dependent patients, the date of MER is the beginning date of the time interval of transfusion independence that has been sustained for at least eight weeks.

Time to MER will be compared between lenalidomide monotherapy and combined treatment of lenalidomide and epoetin alfa in MER responders, using a one-sided log-rank test at the significance level of 0.025. Data from a prior study, MDS-001, of patients with MDS show that the median to MER is 11.5 weeks for patients on the lenalidomide schedule of 10 mg/day for 21 days (10). Under the assumption that the proportions of major erythroid responders are 30% for the monotherapy and 50% for the combined therapy, the log-rank test will have 80% power to detect a hazard ratio of 1.88 of the combined therapy over the

monotherapy. If time to MER follows an exponential distribution, this difference corresponds to an improvement in median time to MER from 11.5 weeks to 6.1 weeks.

Duration of MER response is defined as the time interval between the documented date of MER and the earliest date of resumption of RBC transfusions ≥ 2 units in an 8 week period, a reduction in hemoglobin concentration ≥ 2 g/dL in the absence of acute infection, gastrointestinal bleeding and hemolysis, or death.

Duration of MER response will be summarized by Kaplan-Meier method for patients who achieve MER by treatment arms. A secondary analysis will be done on duration of MER response by excluding all patients on arm B whose epoetin alfa treatment was interrupted by the drug supply issue occurred in September 2010.

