The 90% confidence interval of the rate of MER to salvage combination therapy will be computed in patients who fail to achieve an MER with lenalidomide monotherapy and cross over to the combination therapy. Since it is assumed that the MER rate on the monotherapy arm is 30%, 74 patients from the monotherapy arm will fail to achieve MER. If among them 60 patients cross over to the combination therapy arm, the 90% confidence interval of the MER rate of the 60 patients will be no wider than 22.5%. A secondary analysis will be done on the rate of MER to salvage combination therapy by excluding those cross over patients whose epoetin alfa treatment was interrupted by the drug supply issue occurred in September 2010.

The minor erythroid response rate will be compared between treatment arms by Fisher's exact test. In a prior study MDS-001 of patients with MDS, 2 minor erythroid responses were observed from 17 patients who were on the lenalidomide schedule of 10 mg/day for 21 days (10). If the minor erythroid response rate is 10% for the monotherapy arm and 30% for the combination therapy arm, there is 94% power to detect this difference at a two-sided significance level 0.05.

Cytogenetic response rate will be calculated by treatment arm among patients with cytogenetic abnormalities, along with its 90% confidence interval. If 45% of patients are expected to have genetic abnormalities, the 90% confidence interval of the response rate is no wider than 25.6% for each arm.

Bone marrow response (CR+PR) rate and its 90% Confidence Interval will be calculated by treatment arm. The 90% Confidence Interval of the bone marrow response rate is no wider than 16.8% for each arm.

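### Section 9.3's median time to MER of 11.5 weeks cannot describe responders identified at week 16, and a monotherapy response under way at crossover can be counted as salvage MER

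*Combined protocol and SAP*

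**What the plan says.** **Endpoint and timing.** Sections 6.1.2.3 and 9.2 require MER to last at least 8 consecutive weeks. Section 9.2 fixes the assessment: "The objective MER will be assessed 16 weeks after start of study treatment". The opening of Section 9 gives the same time point alongside the 30% rate and the 20-point goal.

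**Rates.** Section 9.2: "we hypothesize that the MER rate in Arm A (lenalidomide) will be 30" percent, and "anticipate that the MER rate in Arm B (lenalidomide + epoetin alfa) will be at least 50" percent. The 212 patients give about 80% power at an "overall one-sided type I error rate of 0.025".

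**Time to MER.** Section 9.3 analyses responders only. For transfusion-dependent patients "the date of MER is the beginning date of the time interval of transfusion independence that has been sustained for at least eight weeks"; for the others it is the first date of the sustained hemoglobin rise. The planning value from MDS-001 is a "median to MER is 11.5 weeks for patients on the lenalidomide schedule of 10 mg/day for 21 days". With responder proportions of 30% and 50% and exponential times, the plan claims 80% power for a hazard ratio of 1.88, that is, 11.5 weeks falling to 6.1.

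**Salvage.** Arm A patients without MER at week 16 may cross over, and response is assessed at study week 32 (Section 5.2). Section 9.3: "The 90% confidence interval of the rate of MER to salvage combination therapy will be computed in patients who fail to achieve an MER" on monotherapy and cross over. The only baseline defined is the pre-study one: Section 7.1 says counts and transfusions "for the eight weeks prior to randomization are required to establish transfusion-dependence and baseline hemoglobin".

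**The concern.** The duration rule and the assessment time together set a latest onset of about week 8 for anyone scored as a responder. A planning median of 11.5 weeks lies beyond that limit, so the time-to-MER calculation describes patients whom the week-16 rule would not identify.

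The same limit affects crossover. A patient who becomes transfusion-independent in week 10 of monotherapy has not completed 8 weeks at week 16. That patient can be classed as a failure, start epoetin alfa, and be a salvage responder at week 32. By Section 9.3's own dating the response began before the treatment credited with it.

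At stake are the stated power of one secondary comparison (objective 2.2.1) and the meaning of the salvage rate (objective 2.2.3).

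**Working it through.** **1. The plan's own figures reproduce.**
- Primary power: inputs 30% vs 50%, 106 per arm (70% of 106 gives the plan's 74 Arm A failures), one-sided 0.025, continuity correction. Fixed-sample check: (0.20 - 1/106 - 1.96 × 0.0673)/0.0659 = 0.89, power 81.3%. Simulating the seven Table 1 boundaries at 53 to 212 patients (200,000 trials) gives 80.5%.
- Time to MER: 106 × 0.30 + 106 × 0.50 = 85 responders, Arm A share 0.375. √(85 × 0.375 × 0.625) × ln 1.88 - 1.96 = 0.86, power 80.4%. Median: 11.5/1.88 = 6.1 weeks.

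Each calculation is right on its inputs. The conflict is between them.

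**2. Onset limit.** Latest onset = 16 - 8 = week 8. Visit windows, and dating from randomization rather than first dose, move this by days and do not bring it to 11.5.

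**3. Three readings of 9.2 and 9.3.**
- *30% and 50% are week-16 rates.* Every responder has onset by about week 8, so a median of 11.5 weeks is impossible among them. Primary power stands at 80.5%; the 9.3 medians do not.
- *30% and 50% are eventual rates, with times to onset.* Fewer than half of Arm A responders start by week 8 under any distribution, so the week-16 rate is below 15%. With the plan's exponential, F(t) = 1 - 2^(-t/median): F(8) = 0.383 for 11.5 weeks and 0.597 for 6.1 weeks. Arm A is 0.30 × 0.383 = 11.5%. Arm B is 0.50 × 0.597 = 29.9% with the plan's 6.1-week median, or 0.50 × 0.383 = 19.1% if timing equals Arm A. Group-sequential power is 88% or 25% respectively. With the plan's medians, about 12 + 32 = 44 responders would be captured instead of 85. Log-rank power on that count is about 46%. Even this is too favourable, because truncation at week 8 brings the captured medians to 3.5 and 3.1 weeks.
- *11.5 weeks runs to confirmation.* This contradicts 9.3's start-date definition. A 6.1-week median also becomes impossible, since confirmation alone takes 8 weeks. Median onset would be 11.5 - 8 = 3.5 weeks. A hazard ratio of 1.88 would then mean 3.5/1.88 = 1.9 weeks in Arm B.

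**4. Salvage.** Eventual rate 30%, exponential onset, median 11.5 weeks, no epoetin effect:
- Eventual Arm A responders: 106 × 0.30 = 31.8.
- Without MER at week 16: 106 - 31.8 × 0.383 = 93.8.
- Onset in weeks 8-16: 31.8 × (0.619 - 0.383) = 7.5, or 8.0% of 93.8. Applied to the plan's 60 crossovers, that is about 4.8 patients.
- Onset in weeks 16-24, also confirmable by week 32: 12.1 - 7.5 = 4.6.

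With a 3.5-week median onset (confirmation reading), F(8) = 0.795 and F(16) = 0.958. Onset in weeks 8-16 is 31.8 × 0.163 = 5.2 of 106 - 31.8 × 0.795 = 80.7, or 6.4%.

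**The case against.** **The primary rates are week-16 rates.** Section 9 and Section 9.2 both present 30% and 50% for the endpoint assessed at week 16, and nothing calls them eventual. Section 1.2 also reports a pilot with 16 weeks of monotherapy and a 36% erythroid response. That is not MER alone, but it is the nearest 16-week figure. This objection stands.

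A reader might infer that the control rate is really 11.5%, that power is 25%, or that the futility guideline would often stop a useful treatment. The documents do not support this. All of it needs the eventual-rate reading, and the last two also need an 11.5-week median in Arm B, which the plan does not assume. In that case the 20-point guideline is met by the sixth look in 59% of simulated trials; with the plan's own medians it is about 4%, and power rises to 88%. The effect on power has no fixed direction.

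**The 11.5 weeks is weak evidence.** It comes from an MDS-001 schedule group given as 17 patients, in a trial that included 5q31.1-deletion patients. How that trial dated MER is not stated. This limits any claim about the true rates, but it does not remove the mismatch, because the plan itself adopts the figure.

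**Section 9.3 may include later MERs.** Minor responders may stay on assigned treatment (Section 5.1.3), so some later MERs could be seen. Then 9.3's responders are not the week-16 responders, and 30% and 50% are the wrong proportions for it.

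**Salvage misattribution is possible, not certain.** Crossover is optional. A patient with at least a 50% fall in transfusions can qualify as a minor responder and remain on Arm A. The 8% is therefore what could be misattributed if all non-responders cross over.

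**Conclusion.** The point holds in limited form and should be fixed; it is confined mainly to Section 9.3. The onset limit of about week 8 follows from the plan's rules without distributional assumptions. Medians of 11.5 and 6.1 weeks therefore cannot belong to the same 30% and 50% of patients as the primary endpoint, and the stated 80% power for time to MER has no consistent basis.

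The 80% primary power is not shown to be wrong. It changes only if the rates are eventual ones, and then in either direction.

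The salvage estimate can absorb responses that began before epoetin alfa. Their size is about 8% of Arm A non-responders under the plan's exponential 11.5-week assumption, or 6.4% with a 3.5-week median onset. Both figures assume 30% is an eventual rate and that crossover is unrelated to response.

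**What to change.** 1. In Section 9.2, state that 30% and 50% are week-16 rates. In Section 9.3, say whether 11.5 weeks includes the 8-week confirmation. Restate the medians and the detectable difference for the onset window observable at week 16, with matching power.
2. In Section 9.3, count a salvage MER only if its start date falls after the first epoetin alfa dose. Report responses already under way at crossover separately, and state whether those patients stay in the denominator. An analysis against the 8 weeks before crossover can be added as a sensitivity analysis, not as a replacement baseline.

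The cost is wording. Hematology is already scheduled weekly for 8 weeks and then every 2 weeks to week 16, and MER scoring needs transfusion dates in any case. No patients or visits are added and the crossover rule is untouched. The salvage rate will be somewhat lower. The start-date rule does not remove late monotherapy responses that begin after crossover (about 4.6 of 93.8 under the same assumptions), so the estimate should still not be read as an epoetin effect alone.

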1.2 Rationale

Ineffective erythropoiesis remains the hallmark of myelodysplastic syndromes (MDS) for which few treatments offer sustained erythropoietic improvement (1). Treatment with rhu-erythropoietin either alone or in combination with myeloid growth factors ameliorates anemia in some patients. However, for those patients with frequent red blood cell (RBC) transfusion needs (> 2 units/month) or elevated endogenous erythropoietin levels (erythropoietin > 500 mU/mL), cytokine therapy is generally ineffective (2-4). Lenalidomide (REVLIMID®) is an oral 4-amino glutarimide derivative of thalidomide that lacks the neurological toxicities of the parent compound. (5-8). Lenalidomide is a potent modulator of ligand-induced cellular response with biological effects that range from potentiation of antigen-initiated immune response, to modulation of integrin affinity and suppression of trophic response to angiogenic molecules. In AML cell lines, lenalidomide suppresses VEGF transcription, whereas in normal and malignant erythroid progenitors, lenalidomide potentiates clonogenic response to rhu-erythropoietin. In the UT7 erythroid progenitor cell line and in MDS erythroid progenitors, lenalidomide potentiates clonogenic response to rhu-erythropoietin by augmenting ligand-induced activation of STAT5 (9), indicating that erythropoietic response to lenalidomide is erythropoietin-dependent.

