6.1.2.3 Hematologic Improvement

Improvements must last ≥ 8 consecutive weeks.

1. Erythroid Response

- **Major Erythroid Response:** Transfusion-independence for ≥ 8 consecutive weeks for patients who were RBC transfusion-dependent at baseline AND a ≥ 1 g/dL hemoglobin rise compared to mean pre-transfusion baseline value; or a > 2 g/dL rise in hemoglobin without transfusion for non-transfusion dependent patients.
- **Minor Erythroid Response:** The mean hemoglobin is sustained 1.0 to 2.0 g/dL above the baseline value for a minimum of 8 weeks; or a 50% or greater decrease in 8-week RBC transfusion requirements compared to baseline.

2. Platelet Response

- **Major Platelet Response:** For patients with a pretreatment count $< 100,000/\text{mm}^3$, an absolute increase of $\geq 30,000/\text{mm}^3$; for platelet transfusion-dependent patients, stabilization of platelet counts and platelet transfusion independence.
- **Minor Platelet Response:** For patients with a pretreatment platelet count $< 100,000/\text{mm}^3$, a $> 50\%$ increase in platelet count with a net increase $> 10,000/\text{mm}^3$ but $< 30,000/\text{mm}^3$.

Rev. 6/11

3. Neutrophil Response

- Major Neutrophil Response: For pretreatment ANC < 1500/mm³, ≥ 100% increase, or an absolute increase of ≥ 500/mm³, whichever is greater.
- Minor Neutrophil Response: For ANC > 1500/mm³ before therapy, ANC increase of at least 100%, but absolute increase less than 500/mm³, lasting greater than 8 weeks (56 days).

Rev. 10/09

4. Progression/Relapse Following Erythroid Hematologic Improvement

- For patients who achieve RBC transfusion independence: requirement for ≥ 2 units RBC transfusion in an 8 week period or a reduction in hemoglobin concentration by ≥ to 2 g/dL in the absence of acute infection, gastrointestinal bleeding, hemolysis, etc., reaching a hemoglobin < 9.5 g/dL.
- For patients who achieve ≥ 50% decrease in RBC transfusions: return to pre-treatment RBC transfusion requirement over an 8 week period.

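### Baseline transfusion dependence selects each patient's MER rule but is only partly balanced and is left out of the primary comparison, at a modest cost in precision

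*Combined protocol and SAP*

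**What the plan says.** **Primary comparison.** Section 9.2 gives the analysis set, "The primary comparison of the MER rates will be performed on all patients randomized before May 19, 2010 and after September 24", which leaves 212 of the 226 randomized. The target is an "improvement of 20% in the MER rate from 30% to 50%, comparing Arm A to Arm B", "with an overall one-sided type I error rate of 0.025", under a "sequential design for binomial distribution with continuity correction". Section 9.2 names no test. Section 9.4 speaks only of a standardized statistic comparing two MER rates.

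**Response rule.** Section 6.1.2.3 scores transfusion-dependent patients on at least 8 weeks free of transfusion plus a hemoglobin rise of at least 1 g/dL. For all others the rule is "or a > 2 g/dL rise in hemoglobin without transfusion for non-transfusion dependent patients". Section 9.2 repeats the split but omits the 1 g/dL rise for dependent patients.

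**Baseline data.** Section 7.1: "All CBCs and RBC transfusion values for the eight weeks prior to randomization are required to establish transfusion-dependence and baseline hemoglobin".

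**Randomization.** Section 4.3 and the opening of section 9 list two stratification factors, serum erythropoietin (cut at 500 mU/mL) and prior erythropoietin/DA. Transfusion dependence is not one of them.

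**Background.** Section 1.2 says that cytokine therapy seldom works "for those patients with frequent red blood cell (RBC) transfusion needs (> 2 units/month) or elevated endogenous erythropoietin levels".

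**The concern.** MER is in effect two endpoints under one name, and baseline transfusion status decides which one a patient must meet. The chance of success may well differ between the two groups. If so, a comparison that ignores the grouping carries between-group variation in its standard error, and a chance difference in the dependent share shifts the observed arm difference in that particular trial. Both can be reduced with data the trial already requires.

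The plan shows concern for power elsewhere: after the drug-supply interruption it raised the number randomized from 212 to 226 to protect the primary comparison. Section 12.1 says that the trial will support a marketing application. In that setting, a covariate chosen after the data are seen is open to challenge, so any adjustment should be written down beforehand.

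**Working it through.** **1. The plan's own figure.** Inputs from 9.2: 30% vs 50%, one-sided 0.025, "a sample size of 212 cases will provide approximately 80% power to detect improvement in MER rate". Equal allocation is assumed (29 and 28 randomized at the suspension).
- Fixed design without continuity correction: n = (1.96·√0.48 + 0.8416·√0.46)² / 0.20² = 93 per arm.
- With the correction: (93/4)·(1 + √(1 + 4/(93·0.20)))² = 103 per arm, 206 in total.
- Simulating the Table 1 boundaries gives overall alpha 0.0251. Power at 106 per arm with the correction is 0.797 (pooled variance) or 0.809 (unpooled).

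The stated design reproduces.

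**2. Crude standard error.** √[(0.3·0.7 + 0.5·0.5)/106] = √(0.46/106) = 0.066, or 6.6 points.

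**3. Gain from adjusting for dependence.** The dependent share q and the odds ratio for MER (non-dependent vs dependent) are assumptions. Rates within each group are solved so that the arm totals stay at 30% and 50%. The variance ratio (VR) is the adjusted over the crude variance of the risk difference. Power, anchored at 0.80, is Φ(2.8016/√VR − 1.96).

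Worked case, q = 0.65 and odds ratio 2: dependent 24.8%/44.0%, non-dependent 39.7%/61.1% (Arm A/Arm B).
- Within-group variance, Arm A: 0.65·0.248·0.752 + 0.35·0.397·0.603 = 0.205.
- Arm B: 0.65·0.440·0.560 + 0.35·0.611·0.389 = 0.243.
- VR = (0.205 + 0.243)/0.46 ≈ 0.975; the term for unequal risk differences between groups is negligible.
- Power = Φ(2.837 − 1.96) = 0.810. Equivalent N = 212·0.975 ≈ 207.

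Variance ratio and power over the whole range:

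| Dependent share | OR 1.5 | OR 2 | OR 3 | OR 4 |
|---|---|---|---|---|
| 50% | 0.991, 0.804 | 0.973, 0.811 | 0.935, 0.826 | 0.900, 0.840 |
| 65% | 0.991, 0.803 | 0.975, 0.810 | 0.937, 0.825 | 0.903, 0.839 |
| 80% | 0.994, 0.802 | 0.982, 0.807 | 0.955, 0.818 | 0.930, 0.828 |
| 90% | 0.996, 0.801 | 0.990, 0.804 | 0.974, 0.810 | 0.960, 0.816 |

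In the central case (65%, odds ratio 2 to 3), equivalent N is 207 to 199, a saving of 5 to 13 patients.

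**4. Chance imbalance.** Under simple randomization with q = 0.65, the SD of the difference in dependent share is √(2·0.65·0.35/106) = 6.6 points. A two-SD imbalance moves the crude difference by 2.1 points (odds ratio 2; average gap 16.0 points) or 3.3 points (odds ratio 3; average gap 25.2 points). The target is 20 points.

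**5. Error rates.** 400,000 simulated trials per scenario (shares 50%, 65% and 80%; odds ratios 2 and 3), fixed design, no continuity correction:
- Unadjusted one-sided type I error: 0.0246 to 0.0255.
- In the 2.4-3.2% of trials with about a two-SD or larger imbalance favouring Arm B: 0.048 to 0.075 unadjusted, 0.024 to 0.027 with Cochran-Mantel-Haenszel.
- Power: 0.849 to 0.850 unadjusted, 0.855 to 0.871 with Cochran-Mantel-Haenszel.

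**The case against.** **Stratification already covers part of this.** That stands. Section 3.1.1.5.2 admits erythropoietin-naive patients without del 5q31.1 only if they receive at least 2 units a month, so the naive stratum is entirely dependent and imbalance can arise only among prior-erythropoietin patients. The SD in step 4 is therefore an upper figure. For example, at a 50% dependent share, simple randomization gives 6.9 points. If 30% of patients are naive (an assumption), the dependent share among the rest is 0.20/0.70 = 0.286, and the SD falls to √(2·0.70·0.286·0.714/106) = 5.2 points. The mix within the prior-erythropoietin stratum remains unbalanced by design.

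**Prognostic value is not shown for these regimens.** This also stands. A reader might infer from section 1.2 that transfusion need is an established determinant of MER in this trial. That passage concerns cytokine therapy, and both arms receive lenalidomide. Section 1.2 also reports frequent MER on lenalidomide in patients who had failed erythropoietin or had high endogenous levels and a high transfusion burden. No section gives MER by transfusion status.

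**The plan does not commit to an unadjusted test.** True: it names no test for MER at all, so use of the two stratification factors is equally open. The gap is in what is prespecified.

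**A model may be fragile early.** Fair. The first look has 53 patients. The remedy should therefore be kept small.

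**Conclusion.** The point holds as a modest loss of precision. With a dependent share of 50-90% and an odds ratio of 1.5-4, adjusting for dependence alone gains about 0 to 4 power points, or 1 to 21 patient-equivalents (central case 1 to 2.5 points, 5 to 13 patients). Both ranges are assumptions. Any further gain from baseline hemoglobin is not quantified.

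Two stronger readings are tempting, and the documents support neither:
- *That ignoring dependence makes the primary test invalid.* Chance imbalance is already part of the crude standard error, and overall type I error stays near 0.025. The higher conditional error in step 5 belongs to a small fraction of trials. It bears on how convincing one result is, not on the validity of the procedure.
- *That adjustment would lift power to 85-90%.* Exceeding 85% needs about 13% of the outcome variance explained, since Φ(2.8016/√0.87 − 1.96) = 0.85; reaching 90% needs about 25%. The largest share in the table is 10%. At a 50% dependent share even a 40-point gap between groups gives only 87%, and in Arm A that means 10% vs 50%, an odds ratio of 9. Nothing in the documents supports such effects.

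**What to change.** 1. First reconcile sections 6.1.2.3 and 9.2 on the 1 g/dL rise for dependent patients, so that the endpoint being modelled is settled.
2. In 9.2, prespecify the primary comparison as a Cochran-Mantel-Haenszel test with a Mantel-Haenszel risk difference, or a standardized logistic risk difference. Include baseline transfusion dependence and the two stratification factors. Mean pre-transfusion hemoglobin may be one optional added covariate. Leave out RBC units, which largely define dependence.
3. In 9.4, use the same statistic at every look, with a written rule for collapsing sparse strata. Under 3.1.1.5.2 naive patients are all dependent with erythropoietin above 500 mU/mL, so they fill one cell and the prior-erythropoietin patients fill four. Five occupied cells at 53 patients average 10.6 each, about five per arm.
4. Keep N = 212 and the unadjusted difference as a sensitivity analysis. Report MER by arm within dependent and non-dependent patients.

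Cost: protocol wording, some programming, and a check of the new statistic against the Table 1 boundaries, which were set for a continuity-corrected binomial comparison. No added patients, visits or data. The downside is a slightly more complex statistic at the small early looks.
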